9.0 SERIOUS ADVERSE EVENT REPORTING

This protocol does not contain investigational agent(s), and adverse events occurring as a result of this commercially available treatment should be reported to CCTG in the manner described below. In addition, your local Research Ethics Board (REB) should be notified.

The descriptions and grading scales found in the NCI Common Terminology Criteria for Adverse Events (CTCAE) will be utilized for Adverse Event (AE) reporting (version can be found in Appendix IV). All appropriate treatment areas should have access to a copy of the CTCAE. A copy of the CTCAE can be downloaded from the CTEP web site: (http://ctep.cancer.gov/protocolDevelopment/electronic_applications/ctc.htm).

All serious adverse events (SAE) defined as per ICH guidelines (see below) and other adverse events must be recorded on case report forms. In addition, all “reportable” serious adverse events are subject to expedited reporting using the CCTG SAE form. The term ‘reportable SAE’ is used in the definitions which follow to describe those SAEs which are subject to expedited reporting to CCTG.

9.1 Definition of a Reportable Serious Adverse Event

- All serious adverse events which are unexpected and related to protocol treatment must be reported in an expedited manner (see Section 9.2 for reporting instructions). These include events occurring during the treatment period (until 30 days after last protocol treatment administration) and at any time afterwards.
- Unexpected adverse events are those which are not consistent in either nature or severity with information contained in the product monograph or package insert.
- Adverse events considered related to protocol treatment are those for which a relationship to the protocol agent cannot reasonably be ruled out.
- A serious adverse event (SAE) is any adverse event that at any dose:
 - results in death
 - is life-threatening
 - requires inpatient hospitalization or prolongation of existing hospitalization (excluding hospital admissions for study drug administration, transfusional support, scheduled elective surgery and admissions for palliative or terminal care)
 - results in persistent or significant disability or incapacity
 - is a congenital anomaly/birth defect

Medical and scientific judgement should be exercised in deciding whether expedited reporting is appropriate in other situations such as important medical events that may not be immediately life-threatening or result in death or hospitalization but may jeopardize the patient or may require intervention to prevent one of the events listed above.

9.2 Serious Adverse Event Reporting Instructions

All reportable serious adverse events must be reported using a web-based Electronic Data Capture (EDC) system being used for this trial. For details about accessing the EDC system and completing the on-line SAE report form, please refer to the CCTG Generic Data Management Guidebook for EDC Studies posted on the HN.10 section of the CCTG website (www.ctg.queensu.ca).

Within 24 hours: Complete preliminary Serious Adverse Event Report and submit to CCTG via EDC system.

Within 10 days: Update Serious Adverse Event Report as much as possible and submit report to CCTG via EDC system.

EDC SAE web application interruption:

In the rare event that internet connectivity to the EDC SAE system is disrupted, please print and complete a paper copy of the SAE Report, available from the trial specific website

FAX paper SAE Report to:

HN.10 Study Coordinator
Canadian Cancer Trials Group
[contact]

Please use the same timelines for submission as for direct EDC reporting.

Once internet connectivity is restored, the information that was FAXED to CCTG on the paper SAE Report must also be entered by the site into the EDC SAE web application.

Local internet interruption:

If you are unable to access the EDC SAE system, and cannot access a paper copy of the SAE Report from the trial website, please phone the HN.10 trial team [contact]) to obtain a copy of the SAE Report by FAX. Once completed, the report must be FAXED back to CCTG as indicated above. Once internet connectivity is restored, the information that was FAXED to CCTG on the paper SAE Report must also be entered by the site into the EDC SAE web application.

In cases of prolonged internet interruptions, please contact the CCTG Safety Desk for further instructions [contact]).

9.3 Other Protocol Reportable Events – Pregnancy Reporting and Exposure Reporting

9.3.1 Pregnancy Prevention

Women of Childbearing Potential (WOCBP) and males who are enrolled in the trial must have agreed to use contraceptive method(s) as described in Eligibility Criterion 4.1.10. Investigators may wish to additionally advise the female partners of male participants about pregnancy prevention guidelines when appropriate and compliant with local policy.

9.3.2 Pregnancy Reporting

The investigator is required to report to CCTG any pregnancy occurring in female participants and female partners of male participants. Pregnancies occurring up to 6 months for female participants and up to 24 months for female partners of male participants after the completion of study treatment must also be reported.

The investigator should report the pregnancy in a timely manner, within 24 hours of learning of the pregnancy using the CCTG Pregnancy Reporting Form available from the trial webpage, under the “Toolbox” link.

Once informed consent has been obtained, the form should be updated to provide further pregnancy information and to reflect the outcome of the pregnancy. All follow-up reports must be submitted to CCTG in a timely manner. For pregnant partner of trial participant (and pregnant participants, if required by local policy), a copy of the signed signature page of the pregnancy follow-up consent must be submitted to CCTG.

Documents outlined above (including updates) must be sent to the CCTG safety desk [contact]/ [contact]).

If the pregnancy results in death (e.g. spontaneous abortion, stillbirth); is life-threatening; requires inpatient hospitalization or prolongation of existing hospitalization; results in persistent or significant disability/incapacity; is a congenital anomaly/birth defect, then an SAE report must be additionally submitted as described above. Please note, hospitalization for labour/delivery alone does not constitute an ‘inpatient hospitalization’ for the purposes of pregnancy reporting.

9.3.3 Exposure Reporting (Non-study Participants)

The investigator is required to report to CCTG any incidence of exposure to study agent(s). Exposure is defined as significant, direct, contact/inhalation/consumption of agent(s) by non- study participant (an individual who is not otherwise participating in this clinical trial). An example of an exposure includes a non-study participant swallowing study medication. The investigator is responsible for determining significance, based on the agent to which the individual is exposed.

The investigator should report the exposure in a timely manner, within 24 hours of learning of the exposure, using the CCTG Exposure Reporting Form available from the trial webpage, under the “Toolbox” link.

Once informed consent has been obtained, the form should be updated to provide further exposure information and to reflect the outcome of the exposure as the information becomes available upon appropriate follow-up of the exposed individual for a period of 30 days. All follow-up reports must be submitted to CCTG in a timely manner. A copy of the signed exposure follow-up consent signature page must also be submitted to CCTG.

Documents outlined above (including updates) must be sent to the CCTG safety desk ([name]/ [contact]).

If the exposure results in death; is life-threatening; requires inpatient hospitalization or prolongation of existing hospitalization; results in persistent or significant disability/incapacity; is a congenital anomaly/birth defect, then an SAE report must be additionally submitted as described above.

9.4 CCTG Responsibility for Reporting Serious Adverse Events to Health Canada

The CCTG will provide expedited reports of SAEs to Health Canada for those events which meet regulatory requirements for expedited reporting, i.e. events which are BOTH serious AND unexpected, AND which are thought to be related to protocol treatment (or for which a causal relationship with protocol treatment cannot be ruled out).

9.5 Reporting Serious Adverse Events to Investigators

CCTG will notify Investigators of all serious adverse events from this trial that are reportable to regulatory authorities in Canada as reported to CCTG. This includes all serious events that are unexpected and related (i.e. possibly, probably, or definitely) to protocol treatment. The reports will be posted to the CCTG trial HN.10 web-based safety monitoring utility. Investigators must review and document in the trial files proof of review of these events as per ICH GCP.

Investigators must notify their Research Ethics Boards (REBs) of events which involve corrective action(s) to be taken as a result of the event(s) such as protocol and/or informed consent changes and any other event required by their REB. The date of REB Submission for these SAEs will need to be entered into the CCTG trial HN.10 web based safety monitoring utility and documentation of REB submission must be retained in the study binder on site. The REB submission template provided by CCTG can be used to assist with tracking, submission, filing and monitoring.

The submission of events to your ethics board should be done as soon as possible (we suggest within 30 days). REB submissions greater than 90 days from the date of notification will be regarded as delinquent and a major deficiency will be assigned. These safety reports are to be filed in the trial files on site.

10.0 PROTOCOL TREATMENT DISCONTINUATION AND THERAPY AFTER STOPPING

10.1 Criteria for Discontinuing Protocol Treatment

Patients may stop protocol treatment in the following instances:

- Intercurrent illness which would, in the judgement of the investigator, affect assessments of clinical status to a significant degree, and require discontinuation of protocol therapy.
- Unacceptable toxicity as defined in Section 7.0.
- Disease progression, recurrence, or treatment failure as defined in Section 8.4.6.
- Request by the patient.
- Completion of therapy as outlined in Section 7.0. Efforts should be made to maintain the investigations schedule and continue follow-up, even if patients discontinue protocol treatment prematurely and/or no longer attend the participating institution.

10.2 Therapy After Protocol Treatment is Stopped

At the discretion of the investigator.

10.3 Follow-up Off Protocol Treatment

Please see Section 5.0.

For phase Ib and phase II studies, continued follow up after progression (on treatment or during follow up), using an abbreviated form (including subsequent therapies) every 6 months is required until CCTG advises centres that the final analysis has been performed and follow up can be discontinued. If patient is unable to return to participating centre for follow up, please contact CCTG to discuss possible options prior to considering 'withdrawal of consent' processes. Remote oversight allowing data submission may be feasible.

Final report (Form 6) will be required only on patients who die during protocol therapy, within 30 days after last dose, or within the protocol defined follow-up period for patients as above. Due within 2 weeks of knowledge of death (see Appendix III - Documentation for Study).

11.0 CENTRAL REVIEW PROCEDURES

11.1 Central Data Review

CCTG receives core support from the Canadian Cancer Society. To ensure efficient use of limited funding, the CCTG has, over the past 40 years, optimized their risk based trial oversight and monitoring program. A critical component is central data review of submitted deidentified source documents, allowing source data verification and confirmation of key aspects including eligibility, endpoints and safety outcomes. Depending on the trial's design, these source documents may include such source documents as surgical and histopathology reports to confirm disease stage and type, imaging reports to confirm extent of disease and assess efficacy, or include submission of tumour samples (to confirm diagnosis and eligibility or DICOM images (to verify response or radiation therapy planning). These source documents are reviewed by experienced data managers and physicians and are critical to ensuring the accuracy of the data and consistency of conclusions drawn.

The collection of this critical data involves uploading documents through the password protected and secure CCTG electronic Supporting Document Upload Tool (SDUT) data capture linked system. See Appendix III (Documentation for Study) for details of supporting document requirements for this trial and for requirements for the redaction of personal identifiers. Although it remains the centres responsibility to ensure adequate redaction of any information provided to CCTG, submitted source documents are reviewed prior to acceptance at CCTG; in the case of incomplete redaction, documents are removed and the site assigned a violation and required to resubmit.

All patients will provide written informed consent for submission of source documents, and the rationale and documents to be collected will be detailed in the informed consent document.

11.2 Central Radiology Review

For any patient with local-regional failure, central radiology review will be performed to confirm site of failure. Please refer to Section 7.2.18.

11.3 Central Pathology Review

There will be no central pathology review for this study.

11.4 Central Radiotherapy Review

All patients will undergo central review of radiotherapy contours and plans. Please refer to Section 7.2.17.

12.0 CORRELATIVE STUDIES

When considering the implementation of de-escalated treatment approaches such as the reduction of radiotherapy treatment volumes, it is important to be able to accurately categorize a patient's prognosis. Currently, risk stratification for HPV-related OPSCC relies primarily on clinical stage. We will evaluate 4 putative prognostic biomarkers to assess their prognostic significance in this cohort of low-risk patients receiving de-escalated treatment. These putative prognostic biomarkers are: 1) a 4-feature radiomic signature; 2) HPV genotype in tumour tissue; 3) *TP53* mutation with chromosome 3p deletion; and 4) HPV DNA levels in baseline plasma cell-free DNA. The association of each putative prognostic biomarker with EFS will be determined using the Cox proportional hazards method. Discriminative performance of the putative prognostic biomarkers will be compared with each other and with clinical features using the concordance index.

A detailed Correlative Studies Manual will be provided on the HN.10 trial specific website, which will include details regarding sample preparation, handling and shipping.

Specimens collected may be used by researchers now or in the future to better understand the nature of HPV-related OPSCC and how patients respond to treatment. Samples will be used for research purposes only and will not be sold. Patients will not be identified by name. The only identification of tissue will be by a patient study number assigned at the time of registration to the trial the surgical/ histology number and/or patient initials. Material issued to researchers will be anonymized and only identified by a coded number.

Testing for hereditary genetic defects predisposing to malignant disease will not be carried out.

All patients on whom a diagnostic tumour block is collected will be aware of this retrieval and will have given their consent.

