12.1 Protocol-Mandated Correlative Studies

Radiologic Image and RT Structure Collection:

The submission of a RT planning CT scans with associated contours is mandatory for participation in this trial.

The association of a published radiomic signature with EFS will be determined in this population of HPV-related OPSCC patients treated with reduced ENI volumes. Specifically, the 4-feature radiomic signature of Aerts et al./*Aerts 2014*/ will be derived from each gross tumour volume contour using PyRadiomics or comparable software.

Tumour Tissue Collection:

The submission of a representative block of the diagnostic tumour tissue at the request of the CCTG Central Tumour Bank is mandatory for participation in this trial. One tumour block is requested from a biopsy of the primary oropharyngeal tumour. If no primary cancer blocks are available, one block of metastatic lymph node tissue can be sent instead. Where local centre regulations prohibit submission of blocks of tumour tissue, the approval of the CCTG must be sought prior to registration of the first patient to allow cores (two 2 mm cores of tumour from the block) and a predetermined number of slides of representative tumour tissue to be substituted in response to the Central Tumour Bank request.

Somatic mutations and HPV genotype will be detected within tumour DNA in order to determine their prognostic significance in patients treated with reduced ENI volumes. Genomic DNA will be extracted from tumour blocks and peripheral blood leukocytes (germ line) and will be subjected to high throughput sequencing using published methods [Newman 2014]. Briefly, DNA libraries will be constructed from tumour genomic DNA and germline genomic DNA. Targeted sequencing will be performed in order to detect frequent OPSCC-associated HPV genotypes as well as mutations within TP53 and genetic deletions within FHIT (chromosome 3p14 marker).

Blood and Plasma Collection:

The submission of whole blood and plasma is also mandatory for participation in this trial.

Whole blood will be used as a source of germ line DNA (from peripheral blood leukocytes) for targeted sequencing of the TP53 and FHIT genes and comparison with tumour DNA as described above.

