13.3 Sample Size and Duration of Study

We estimate 2-year EFS to be 91% (H_a) for low-risk HPV-related OPSCC. Assuming that the experimental treatment will be considered as ineffective if the 2-year EFS is $\leq 85\%$ (H_0), with one-sided alpha of 0.1, a sample size of 100 patients will have 80% power to detect a 6% difference of 2-year EFS. With 3 years of accrual and 2 years of follow-up, the total duration of this study will be 5 years. A total of 304.7 person-years of follow-up is needed for the final analysis. The null hypothesis (H_0) will be rejected when the observed survival rate is 88.85% or higher (i.e. if there are 18 or fewer EFS events observed).

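### Biomarkers and clinical features are compared by concordance index in the fitting cohort with about 14 expected events and no stated optimism correction or interval, so multi-parameter models would look too good and differences would be very imprecise

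*Protocol*

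**What the plan says.** Protocol section 12.0 sets the aim: "We will evaluate 4 putative prognostic biomarkers to assess their prognostic significance in this cohort of low-risk patients receiving de-escalated treatment". The four are a radiomic signature, HPV genotype in tumour, TP53 mutation with 3p deletion, and baseline plasma HPV DNA. Two sentences give the analysis: "The association of each putative prognostic biomarker with EFS will be determined using the Cox proportional hazards method", followed by "Discriminative performance of the putative prognostic biomarkers will be compared with each other and with clinical features using the concordance index". Section 12.1 adds for imaging: "The association of a published radiomic signature with EFS will be determined in this population of HPV-related OPSCC patients treated with reduced ENI volumes".

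The clinical features are not listed, and no second cohort, resampling or interval for the index is mentioned. SAP section 1.1 repeats prognostic biomarkers as a secondary objective, but SAP sections 2.1 to 2.8 and Tables 1 to 21 contain no biomarker analysis. The two sentences in section 12.0 are therefore essentially the whole plan for the comparison.

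The information available follows from Protocol section 13.3: "We estimate 2-year EFS to be 91% (H_a) for low-risk HPV-related OPSCC", and "A total of 304.7 person-years of follow-up is needed for the final analysis". SAP section 1.6 puts 99 eligible patients in the efficacy analysis.

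**The concern.** A concordance index computed on the patients used to fit the model is optimistic, and the optimism grows as parameters are added and events become fewer. Indices from a one-parameter marker model and a multi-variable clinical model are then not on one scale. A clinical model with no real information could appear to match or beat a marker that has some. Separately, with so few events even unbiased indices differ widely by chance, and without intervals a reader could not tell signal from noise. At stake is the interpretation of a secondary objective, namely whether any of the four markers adds to clinical staging in patients given reduced treatment volumes.

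**Working it through.** **1. The plan's own figures.** With exponential EFS, hazard = −ln(2-year EFS)/2.
- Alternative: −ln(0.91)/2 = 0.04716 per year. Null: −ln(0.85)/2 = 0.08126 per year.
- The stated cut-off of 18 events gives exp(−2 × 18/304.7) = 88.86%, against 88.85% in section 13.3.
- Under the null the expected count is 0.08126 × 304.7 = 24.8, and the Poisson probability of 18 or fewer is 0.0999, which matches alpha 0.1.
- Under the alternative the probability of 18 or fewer is 0.861 (0.829 allowing for the futility stop). The stated 80% corresponds to 17 or fewer (0.7999). The stated power is thus conservative, which has no bearing on this point.

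**2. Events available.** Under the alternative: 0.04716 × 304.7 = 14.4. Uniform accrual over 3 years plus 2 years of follow-up gives 15.0 for 99 patients. Under the null: about 25.

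**3. Apparent concordance when nothing predicts.** Simulation assumptions: 99 patients, exponential times, censoring uniform between 2 and 5 years, about 14 to 15 events, continuous predictors.

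| Fitted parameters | Mean apparent C (truth 0.50) |
|---|---|
| none (locked score) | 0.497 |
| 1 | 0.564 |
| 2 | 0.596 |
| 4 | 0.642 |
| 6 | 0.674 |
| 8 | 0.702 |

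A single binary marker gives 0.532 at 10% prevalence and 0.553 at 50%. A separate simulation of 400 datasets (mean 14.5 events) gave 0.557 for one parameter, 0.637 for four and 0.506 for a fixed-weight score.

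**4. Dependence on the event count.** Mean null C for 1, 4 and 8 parameters:
- 10 events: 0.569, 0.665, 0.735
- 14 events: 0.562, 0.650, 0.708
- 18 events: 0.556, 0.629, 0.683
- 25 events: 0.551, 0.617, 0.664

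**5. Noise model against a real one-parameter marker.** Percentage of runs in which the noise model has the higher apparent C:

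| HR per SD of the real marker | 4 parameters | 6 | 8 |
|---|---|---|---|
| 1.5 | 62 | 76 | 85 |
| 2.0 | 32 | 44 | 57 |
| 2.5 | 13 | 24 | 35 |

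**6. Among the four biomarkers, no signal, 14 events, 600 runs.** With the radiomic signature as one score it has the highest C in 232 runs (39%), against 247 (41%) for plasma HPV DNA; two binary markers at an assumed 10% prevalence share the rest. If its four features were refitted, it would come first in 497 runs (83%).

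**7. Precision.** At 14 events the SD of C for a locked score is about 0.08, and the SD of the difference between two independent locked scores is 0.117. An approximate 95% range for a difference with no true effect is ±1.96 × 0.117 = ±0.23.

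**8. What bootstrap correction achieves** (150 null datasets with exactly 14 events, 30 resamples each): 0.564 falls to 0.522 for one parameter, 0.642 to 0.544 for four, and 0.705 to 0.571 for eight. The gap between eight parameters and one falls from 0.14 to 0.05 and does not vanish.

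**9. Sparse binary markers.** With m carriers at average risk, the chance that none has an event is (1 − 14.4/99)^m: 73%, 46% and 21% for m = 2, 5 and 10. The documents give no prevalence, so these counts are a range. With no events among carriers, the ordinary Cox log hazard ratio has no finite estimate and no usable Wald interval.

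**The case against.** The case against is substantial, and much of it limits the size of the problem.

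- A reader might infer that the comparison mainly rewards whichever predictor has most parameters. The documents do not support that. Section 12.1 speaks of one published signature, most naturally one score per patient; only the locking of its weights is unstated. Plasma HPV DNA and TP53 with 3p deletion can each enter as one parameter. Genotype may need more, since section 12.1 covers several types. Step 6 shows little bias between continuous single-score markers; what remains follows scale and prevalence.
- No multi-variable clinical model is specified. The SAP baseline factors are tied to the EFS subgroup table, not to section 12.0, which itself says that risk stratification now rests mainly on clinical stage. T and N stage alone would be about three parameters, and the null C would lie between the values for two and four (0.60 and 0.64). Using all the Table 11 factors except chemotherapy would take nine.
- A reader might infer that a clinical model will beat a true marker. That is conditional on strength: at HR 2.5 per SD, eight noise parameters win in 35% of runs and four in 13%.
- A reader might infer that this analysis decides which marker goes forward for patient selection. Section 12.0 describes a comparison; it gives no ranking or selection rule.
- In-sample, uncorrected use is inferred from silence, although only one cohort is named and no correction is mentioned.

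What does not fall away: followed as written, the plan yields apparent indices that differ in optimism whenever parameter counts differ, and it asks for no measure of uncertainty when differences have an SD of about 0.12.

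**Conclusion.** The point holds as an analysis that should be tightened at little cost, not as a demonstrated bias among the four biomarkers. With about 14 EFS events under the alternative, apparent C with no signal averages about 0.56, 0.64 and 0.70 for one, four and eight fitted parameters, against 0.50 for a locked score. At about 25 events the fitted values are 0.55, 0.62 and 0.66. The bias falls mainly on any multi-variable clinical model set beside a single marker of modest strength. If every biomarker is one locked score, imprecision is the larger limitation.

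These sizes rest on assumed parameter counts, exponential event times, the assumed censoring pattern and predictor distributions, and use of the final-analysis data, since section 12.0 gives no separate timing. The primary EFS decision rule is not affected.

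**What to change.** Add to Protocol section 12.0 or the SAP:

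1. Apply the published radiomic signature as one score with its published weights.
2. Prespecify a small clinical model by naming its variables, and compare each marker with it in the common set of patients who have all markers measured.
3. Report bootstrap optimism-corrected C with 95% CIs, including CIs for differences in C, and note that correction narrows the gap between large and small models without removing it.
4. For sparse binary markers, show events per group and use Firth-penalised Cox regression with profile-likelihood intervals.

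The cost is a paragraph of wording and some computing; no new data are needed. Reported C values will be lower, and the common set will be slightly smaller than the full eligible cohort.
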